### **General Data Analytic Strategies**

All statistical analyses will use SAS v. 9.2 (SAS Institute Inc., Cary, N.C.). Preliminary data analyses inspecting group differences on demographic and baseline variables will evaluate posterior distributions for differences in proportions and means, as well as for correlations between baseline variables and specified outcomes. Baseline or demographic variables for which the posterior distribution indicates there is > 99% chance of a difference across groups, and for which there is a > 99% chance of a non-zero correlation with outcomes, will be defined as potential confounders and will result in two sets of analyses: one in which the relevant variable is included as a covariate and one in which it is not. This will permit determination of the degree to which any group differences might confound conclusions regarding treatment.

Evaluation of the primary outcome, proportion of patients demonstrating > 50% decrease in depression scores on the MADRS, as a function of treatment will use a beta-binomial model and contingency tables with chi-square testing for Bayesian and Frequentist approaches respectively. Additional analyses will use the generalized linear modeling. Count, dichotomous and continuous Bayesian analyses will be conducted using Poisson (Proc GENMOD; SAS 9.2), logistic (Proc GENMOD; SAS 9.2), linear (Proc GENMOD; SAS 9.2) regression respectively. Distributional assumptions will be evaluated via inspection of residual plots and, where possible, by formal statistical tests. Violation of assumptions will be addressed, depending upon statistical technique, through the use of transformations, robust methods, and stratification.

Unless otherwise indicated in the data analytic plan, priors will be specified as neutral and diffuse. The beta-binomial model will use a  $\sim\text{Beta}(1,1)$  prior distribution. For linear, Poisson, and logistic regression, priors will take the form  $\sim\text{N}(0, 1 \times 10^6)$  in the linear, log, and log(odds) scales respectively. Convergence of Bayesian analyses on the posterior distributions via Monte-Carlo Markov chain (MCMC) will be assessed via graphical (Trace Plot, Autocorrelation Plot) and quantitative (Geweke Diagnostics, Gelman-Rubin Diagnostics, and Heidelberger-Welsh Diagnostics) evidence. Evaluation of posterior distributions will permit statements regarding the probability that effects of varying magnitudes exist, given the data.

Interim Bayesian analysis with application of pruning/retention rules will be conducted when 50% of randomized subjects have reached (or should have reached) the end of study. If, at 50% of data gathering, there are additional participants continuing in active treatments that might be pruned, sensitivity analyses will inspect the degree to which potential results from these active patients might alter the conclusions of the interim analysis. If necessary, randomization will be temporarily suspended and data gathering will continue until sensitivity analyses demonstrate that statistical conclusions will remain unchanged by any patients who have not yet completed treatment. While Frequentist approaches require adjustment for multiple testing when conducting interim analyses, no such adjustment is necessary for Bayesian analyses due to its conformity to the likelihood principle [57]. Further, Monte Carlo simulations (conducted in SAS v. 9.2) demonstrate that Type I and Type II Error Rates are at appropriate levels for the proposed design (see Simulation Study). Intention to treat principles will apply at both the interim and final analysis points; any patients having dropped out of the study will be counted as non-responders.

Structural Equation Modeling/Path Analysis will evaluate the degree to which inflammatory cytokines and markers of oxidative stress mediate the effect of treatment on MADRAS. Estimation of SEM/Path Models will employ both Frequentist and Bayesian approaches. In the context of the direct effects of treatment, mediational modeling will permit estimates of the indirect effects of treatment on MADRAS scores via inflammatory cytokines or markers of oxidative stress using the product coefficient method [68]. Frequentist ninety-five percent confidence intervals for maximum likelihood estimates will be constructed using a bootstrap resampling approach [69]. Bayesian SEM estimates for indirect effects will employ the posterior distribution of the product coefficient. All SEM/Path analyses will be conducted in MPlus v. 6.0 [70].

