### **Study Design**

BD type I or II patients (n=160), on a depressive or mixed episode, who were on therapeutic doses of any of the commonly utilized mood stabilizing agents (lithium, anticonvulsants, atypical antipsychotics) for at least one month and who were still symptomatic (MADRAS >20) will be enrolled. Patients will be randomly assigned to orally receive one of 4 conditions: aspirin 1000 mg (2 capsules of 500 mg) qam, NAC 1000 mg (2 capsules of 500 mg) bid, combined aspirin and NAC at same doses as given individually or matched placebo, as an add-on medication to their ongoing treatment regimen, for an 16-week double-blind trial. After the first 8 week of the double blind treatment, the responders will keep taking the same study drug, whichever it is. And the non-responders will be re-randomized for one of the other three groups of study drugs they haven't tried yet.

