If patients qualify for the study initially based on SCID-I interview, physical examination, and routine labs (CBC, liver functions tests, electrolytes, kidney function tests, thyroid function tests, HIV testing, and urinalyses), but are not currently taking an approved psychotropic medication or combinations they are eligible to participate in a lead-in phase. This phase would be starting at their screening visit and last approximately 6 to 8 weeks depending on the patient's mood. During this lead-in phase, either the PI or Co-PI will evaluate the patient and prescribe either Lithium or Depakote. The patient will be monitored during this treatment phase by the PI or Co-PI and will return after two weeks for an evaluation. The evaluation will include CSSR-S and adverse effects. If the patient is prescribed lithium, their lithium levels will be tested. The patient will continue to follow up every two weeks. At the 4 week visit, the patient will also come in for evaluation (CSSR-S and adverse effects). At the 6 week visit, the patient will be re-evaluated for the double-blind study trial. If the patient has been on an adequate dose of the psychotropic medication for at least 4 weeks and score greater than 20 on the Montgomery-Asberg Depression Rating Scale (MADRS), then they will be enrolled. If they do not meet inclusion criteria at the week 6 lead-in phase visit, they will return at Week 8 and be re-evaluated. PI and Co-PI will continue to prescribe the psychotropic medication throughout the lead-in phase (up to 8 weeks) and through the trial (up to 16 weeks).

During the lead-in phase participants will not be compensated. They will receive a voucher for their parking for each visit. They will be responsible for filling and paying for all prescriptions in both the lead-in phase and through the trial (up to 16 weeks).

Upon completion of the first 8-week double-blind trial, patients who responded to the active medication will continued on the same study drug for an additional 8 week double-blind treatment. The non-responders to one of the study drugs will be re-randomized for one of the other three groups of study not received and will remain in treatment for an additional 8 week double-blind treatment. Treatment response will be defined as improvement in the **MADRS scores of at least 50%**.

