During the first 8-week trial, patients will be seen at weeks 0, 1, 2, 3, 4, 6 and 8 for clinical assessment and mood ratings. During the continuation trial, they will be seen at weeks 8, 10, 12, 14 and 16. The main outcome measure for the study will be the scores on the Montgomery-Asberg Depression Rating Scale, MADRAS [62]. All patients will also be assessed with the Young Mania Rating Scale, YMRS [63], the Clinical Global Impression-Bipolar version, CGI-BP [64], and the UKU side-effects scale [65]. In all visits, patients will be seen by the study psychiatrist and the research staff will complete mood ratings with the MADRAS, YMRS, CGI-BD, and the UKU side-effects scale.

At baseline (before randomization), week 8 and week 16 blood will be sampled for proinflammatory markers (C-reactive protein, soluble interleukin (IL)-2 receptor, IL-6 and tumor necrosis factor (TNF)-alpha), and oxidative stress

markers (superoxide dismutase activity and catalase activity, serum thiobarbituric acid reactive substances (TBARS)), which have been reported to be elevated in BD patients [34] [33] [35]. These blood samples will be stored for possible future research on biomarkers or future genetic studies for up to 20 years, for use in pharmacogenetic research during this 20 year timeframe. The samples will be stored at the Wet Lab, in a double locked -80 degrees freezer, at [REDACTED]

[REDACTED] for future use studying factors of Bipolar Disorder. When (or before) the 20 year period ends, the blood sample will be destroyed.

Patients will complete neuropsychological testing at baseline and Week 16. The testing will include CANTAB, WASI, and WRAT assessments and will take approximately 3-4 hours.

At the screening visit, week 8, and week 16 we will also be testing the Lithium levels in all patients that have been prescribed and currently taking the medication for study purposes. This extra test will be conducted for the safety of the patient and more Lithium level tests can be ordered under the PI's discretion throughout the 16 week trial.

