### **Statistical analyses:**

#### Simulation Study

In preparation of this application we conducted a Monte Carlo simulation study to assess the relative merits of the proposed DTL adaptive design over a non-adaptive, parallel-group approach. Specifically, the goal of this study was to demonstrate that the DTL design would result in the maximum number of subjects being treated in the most promising conditions, i.e., appropriate "pruning" of less effective conditions. Simulation scenarios including one that posits no effect across conditions and others, assuming specific anticipated effects, permits evaluation of Type I and Type II Error rates respectively. Sample size for each simulated trial was set at  $n = 160$ . Response to treatment was defined, dichotomously, as  $> 50\%$  decrease in depression score as measured on the MADRS. Specification of effects for the simulations assumed that the rate of response in the placebo condition is 25%, while 1000 mg aspirin qd and 1000 mg NAC bid have comparable effects with response rates of 50% each. The combination of 1000 mg aspirin qd and 1000 mg NAC bid is anticipated to demonstrate an additive effect yielding a 70% response rate. At 50% information gathering, defined as  $n = 80$  subjects having completed the study, a Bayesian interim analysis determined the posterior probability that treatment conferred benefit. Benefit was defined as the absolute difference in response rate for each treatment relative to placebo. The remaining 80 subjects were allocated to the retained (non-pruned) treatments, with the probability of assignment to any given group based on the number of groups continuing in the study.

Pruning/Retention Rules. Simulation scenarios considered a variety of pruning rules that varied in stringency for 1) detecting a clinically decisive difference ( $>10\%$  from placebo), and 2) selecting the best performing treatment. All simulations assumed a  $\sim\text{Beta}(1,1)$  prior distribution for the probability of treatment response in all study conditions. A  $\text{Beta}(1,1)$  prior models values within the range  $[0,1]$  in which all values have the same probability of occurring. This constitutes a vague, neutral prior distribution which reflects uncertainty preceding data accrual. At 50% of data gathering ( $n = 80$ ) the prior (i.e.  $\sim\text{Beta}(1,1)$ ) was updated with data generated from a binomial distribution for each

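### The primary response outcome has no stated visit and the cues conflict between week 8 and week 16, although non-responders change arm at week 8; baseline adjustment is a minor loose end

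*Combined protocol and SAP*

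**What the plan says.** **Outcome.** General Data Analytic Strategies opens its main analysis with "Evaluation of the primary outcome, proportion of patients demonstrating > 50% decrease in depression scores on the MADRS", to be analysed by a beta-binomial model and a chi-square test. No visit is given. Study procedures states "The main outcome measure for the study will be the scores on the Montgomery-Asberg Depression Rating Scale", also without a visit. The response rates assumed in the Simulation Study carry none either.

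**Cues to the visit.** Study procedures defines response as improvement in "MADRS scores of at least 50" per cent, in the paragraph on what happens after the first eight weeks. The Simulation Study and General Data Analytic Strategies use a cut of more than 50%. The simulated interim is set at 80 "subjects having completed the study, a Bayesian interim analysis determined the posterior probability that treatment conferred benefit". General Data Analytic Strategies likewise times the interim at the end of study, in a trial that Study Design describes as 16 weeks.

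**Change of arm.** Study procedures: "The non-responders to one of the study drugs will be re-randomized for one of the other three groups of study not received". Study Design says the same, and adds that responders stay on their drug. Intention to treat applies at the interim and final analyses and dropouts count as non-responders, but the text does not say which randomisation is followed after week 8.

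**Covariates.** Adjustment is reserved for "Baseline or demographic variables for which the posterior distribution indicates there is > 99% chance of a difference across groups" that also show more than a 99% chance of non-zero correlation with outcome. Meeting both conditions "will result in two sets of analyses: one in which the relevant variable is included as a covariate and one in which it is not".

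**The concern.** Response can be read at week 8 or at week 16, and the two answer different questions. At week 8 each patient has received only the first assigned treatment. By week 16, under the plan's own 25% placebo rate, 75% of patients first assigned to placebo would have been moved to an active arm. A comparison by first arm then contrasts strategies of starting on one treatment and switching if it fails. Its expected difference is smaller whenever switched patients respond. The pruning decision uses the same response rates, so it is exposed too. Unless the visit is fixed, the choice stays open until data have been seen.

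The covariate rule raises a smaller question. Baseline MADRS is adjusted for only when chance imbalance is large, and the plan does not say which of the two resulting analyses leads.

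**Working it through.** **1. The plan's own power.** Inputs from Simulation of Operating Characteristics: 0.25 versus 0.50, alpha 0.05 (taken as two-sided), 40 or 60 per arm. Formula, with p̄ the mean of the two rates:

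power = Φ{ [ |p₁ − p₀| − 1.96·√(2p̄(1 − p̄)/n) ] / √([p₀(1 − p₀) + p₁(1 − p₁)]/n) }

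At n = 60: (0.25 − 1.96 × 0.0884)/0.0854 = 0.90, giving 81.6% (stated 81.80%). At n = 40 it gives 64.1% (stated 65%). The figures reproduce as a simple two-group comparison with no switching.

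**2. Week 16 by first arm, all arms open.** Assume week-8 responders keep their response. A switched patient goes with equal chance to each of the other three arms and responds at f times that arm's stated rate. With mᵢ the mean rate of the other three arms:

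wᵢ = pᵢ + (1 − pᵢ) × f × mᵢ

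Scenario 1 at f = 1:
- placebo: 0.25 + 0.75 × 0.567 = 0.675
- single drug: 0.50 + 0.50 × 0.483 = 0.742
- combination: 0.70 + 0.30 × 0.417 = 0.825

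Differences from placebo in percentage points, with power at n = 60:

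| f | Scenario 1 single drug | Scenario 1 combination | Scenario 2 combination |
|---|---|---|---|
| 0 (same as week 8) | 25.0 (82%) | 45 (>99%) | 25.0 (82%) |
| 0.5 | 15.8 (41%) | 30 (93%) | 18.3 (52%) |
| 1 | 6.7 (12%) | 15 (48%) | 11.7 (25%) |

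At f = 0.25 the Scenario 1 single drug has 20.4 points and 61% power.

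**3. Pruned arms closed.** Sixty per arm arises only after pruning: 20 patients from the first stage and 40 from the second. The documents do not say whether pruned arms stay open for re-randomisation. Suppose only placebo and the combination remain for second-stage patients (Scenario 1).
- f = 1, second stage: placebo 0.25 + 0.75 × 0.70 = 0.775; combination 0.70 + 0.30 × 0.25 = 0.775; difference 0. Weighted with the first stage: (20 × 15 + 40 × 0)/60 = 5 points, power 10%.
- f = 0.5, second stage: 0.5125 and 0.7375; difference 22.5 points. Weighted: (20 × 30 + 40 × 22.5)/60 = 25 points, power 81%.

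**4. Covariate rule.** By chance alone, the imbalance condition is met for a given baseline variable in about 1–2% of trials for one pair of arms, 3–6% for any arm against placebo and 5–9% for any of the six pairs. The ranges cover a two-sided 0.01 or 0.02 reading of the 99% threshold at 40 per arm. The correlation condition lowers these further, so baseline MADRS goes unadjusted in over 90% of trials.

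Simulated two-arm comparisons with equal 25% response rates gave an overall unadjusted type I error of 4.9–5.4%. Where imbalance fell just below the trigger (|t| from 1.5 to 2.33, about 11% of comparisons), the unadjusted difference was off by roughly 2, 3–4 and 5–6 points at assumed baseline–improvement correlations of 0.15, 0.3 and 0.5. Adjusting changed power at 25% versus 50% by −0.6 to +0.2 points at correlations up to 0.15, about +1.7 at 0.3 and +5 to +6 at 0.5. The documents give no correlation.

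**The case against.** **The plan is not silent on the visit.** This is fair. Defining response in the week-8 paragraph, and calling weeks 8–16 a continuation, favour week 8. But that definition serves the switching decision and is never called the primary outcome, and the interim timing points the other way. The cues conflict.

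**Week 16 by first arm is still randomised.** This is correct. A reader might infer that such a comparison is invalid. It is not: it validly compares starting strategies and keeps its type I error when all arms are equal. What changes is its meaning and its power.

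**The magnitudes rest on an invented f.** This is also correct, so they are illustrations. The direction is firmer: under the plan's rates, placebo has the most switchers and they move to better arms, so any f above 0 shrinks the contrast. One could argue that the 25%, 50% and 70% rates already include switching, but the Simulation Study describes them as effects of the individual treatments.

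**The covariate rule is pre-specified and mostly harmless.** Largely so. Its purpose is stated, and labelling the regressions as additional suggests that the unadjusted test leads. A reader might infer inflated type I error; the check shows it is about nominal.

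**Two rival primary outcomes?** A reader might also infer this from the reference to MADRS scores. The documents do not support it: simulation, pruning, power and dropout handling all use response, so this is a wording conflict. The difference between at least 50% and more than 50% is small as well: 1.6–2.7% of patients fall exactly at 50% under assumed score distributions.

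**Conclusion.** The visit gap is real and should be closed before the interim. The stated power fits a week-8 outcome. At week 16 by first arm, with responders holding, it is kept only if no switched patient goes on to respond. Under the assumptions above, Scenario 1 single-drug power at 60 per arm ranges from 82% to 12% with all arms open. With pruned arms closed, the Scenario 1 combination falls to 81% at f = 0.5 and 10% at f = 1. The power arithmetic itself is sound.

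The covariate point is a free improvement and no threat to validity. It would reduce conditional bias under chance imbalance, and any precision gain depends on an assumed correlation.

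**What to change.** 1. Define the primary outcome as MADRS response at week 8 by first randomised arm, with one cut-off used throughout. Let Study procedures name MADRS as the instrument.
2. Use that same week-8 outcome for the interim and pruning.
3. State that, for the primary outcome, counting dropouts as non-responders applies to dropout before week 8, so that a week-8 responder who leaves later is classified without doubt.
4. Report weeks 8–16 separately.
5. Replace the two-condition trigger with baseline MADRS as a pre-specified covariate in the additional regression models, and state that the unadjusted beta-binomial and chi-square analysis is primary.

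**Cost.** Mostly wording, since baseline and week-8 MADRS are already collected. The interim trigger moves from end of study to week 8, which is a small operational change as well. The pruning criteria and stated power stay as they are because the unadjusted analysis remains primary. If the sponsor prefers the adjusted model to lead, the simulations and power would have to be redone and pruning aligned with it.

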condition. The posterior distributions of the differences between each treatment and placebo formed the basis of pruning decisions. A decisive difference is defined as occurring if the posterior probability of there being a <10% difference between any of the treatments and placebo was  $< 0.20$ . Another way of saying this is that if there was a >80% chance that the all treatment-placebo differences were <10% then the simulation concluded that the trial had failed to find a decisive difference. If this first rule identified the existence of a decisive difference for any of the treatments, the algorithm then selected the treatment that had the highest posterior probability of conferring benefit (i.e. the  $p(\text{treatment-control} > 0|\text{data})$  for participants. If the algorithm failed to identify a decisive treatment difference, the 1000 mg aspirin condition was retained as the active treatment. This was done to further our established programmatic goal of evaluating the anti-inflammatory effects of aspirin on depression by providing the most precise effect size estimate possible.

Study performance in terms of maximizing patients allocated to the best-performing conditions and for Type I and Type II Error rates are reported for the design under these retention/pruning criteria.

Simulation of Pruning/Retention Rules. Simulation evaluated the pruning rules for three scenarios. Scenario 1 simulated clinical trials with binomial probabilities of response of 0.25, 0.50, 0.50, and 0.70 for placebo, aspirin, NAC and aspirin + NAC respectively. Scenario 2 addressed the situation in which the effect sizes are less optimistic. Scenario 2 posited binomial probabilities of response of 0.25, 0.30, 0.30, and 0.50 for placebo, aspirin, NAC and aspirin + NAC respectively. Scenario 3 simulated clinical trials with binomial probabilities of response of 0.25, 0.25, 0.25 and 0.25 for placebo, aspirin, NAC and aspirin + NAC respectively. Since this last scenario simulates data in which there is no effect, the probability of identifying a decisive effect is an estimate of the Type I Error Rate for the pruning algorithm.

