Simulation of Operating Characteristics. Although Bayesian statistical approaches offer a more efficient means by which to weigh evidence, it is still essential to estimate the probability of making specific types of errors using the current design. We first evaluated, over the course of  $k = 200$  simulated trials with the anticipated effects, how often the design fails to find the posited effect. This yields the equivalent of the Type II Error Rate, with one minus this value corresponding to the power of the design. For Scenario 1,  $k=200$  simulated clinical trials indicated that the probability of identifying a decisive difference was >99%. Including trials for which the algorithm failed to identify a decisive difference as Type II Errors, the selection of the best performing treatment based on the highest posterior probability of benefit identified the combination 82.5% of the time. For Scenario 2,  $k=200$  simulations suggested that the probability of identifying a decisive difference was 98.5%. Counting trials for which the algorithm failed to identify a decisive difference as Type II Errors the selection of the best performing treatment based on the highest posterior probability of benefit identified the aspirin + NAC combination 83% of the time. This corresponds to 84.5% power. Since Scenario 3 simulates data in which there is no effect, the probability of identifying a decisive effect is an estimate if the Type I Error Rate for the pruning algorithm. This final scenario identified a decisive effect in >0.5% of simulated trials. This corresponds to a Type I Error Rate of 0.005.

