If  $N = 160$  participants are randomized across four conditions in a 1:1:1:1 ratio, contrasts for treatment response rates versus placebo will use  $n = 40$  participants per cell. For Scenario 1, assuming  $n = 40$  per group and  $\alpha = 0.05$ , power to detect the difference between the proportions 0.25 and 0.50 is 65%. Using the same assumptions power to detect the difference between the proportions 0.25 and 0.70 is >99%. For Scenario 2, assuming  $n = 40$  per group and  $\alpha = 0.05$ , power to detect the difference between 0.25 and 0.5 is 65%. More generally, for comparison of two independent proportions, sample sizes of  $n = 40$  per group and  $\alpha = 0.05$  provide 80% power to detect a difference between 0.25 and 0.55. Such a sample is underpowered for two of the effects in Scenario 1, and all of the effects in Scenario 2. Recall, however that the proposed Bayesian adaptive design results in altered cell sizes such that the most promising treatment and placebo each receive an average of  $n = 60$  participants. (This is substantiated by the simulation results). Assuming  $n = 60$  participants per group and  $\alpha = 0.05$ , power to detect the difference between 0.25 and 0.50 is 81.80%, while power to detect the difference between 0.25 and 0.70 is > 99%. More generally, a sample of this size provide 80% power to detect the difference between 0.25 and 0.49 with  $\alpha = 0.05$ .

In summary, a Bayesian adaptive approach demonstrates adequate operating characteristics (Type I and II Error Rates) for the current trial. The method results in allocation of more participants to the most effective condition. Finally, the approach permits frequent analyses with more desirable Type I and Type II Error rates.

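### The primary response outcome has two unranked analyses and no final decision threshold, and no Type I error is shown for the final efficacy claim after interim selection

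*Combined protocol and SAP*

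**What the plan says.** All references are to the combined protocol and SAP.

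- **Primary analysis.** Under General Data Analytic Strategies, evaluation of the responder proportion "will use a beta-binomial model and contingency tables with chi-square testing for Bayesian and Frequentist approaches respectively". Neither is ranked, and nothing covers disagreement.
- **Bayesian output.** The prior is Beta(1,1). The plan then says: "Evaluation of posterior distributions will permit statements regarding the probability that effects of varying magnitudes exist, given the data". No effect size or probability is named as success.
- **Interim rule.** The Simulation Study calls a difference decisive "if the posterior probability of there being a <10% difference between any of the treatments and placebo was" below 0.20. It then restates the rule as a failure only when there is more than an 80% chance that all the differences are under 10%. The arm with the highest posterior probability of benefit is kept, with aspirin as the fallback. General Data Analytic Strategies places these pruning and retention rules at the halfway interim.
- **Error rates.** The 0.005 is described as the "Type I Error Rate for the pruning algorithm". General Data Analytic Strategies says of interim multiplicity that "no such adjustment is necessary for Bayesian analyses due to its conformity to the likelihood principle", and that simulated Type I and II rates are appropriate for the design.
- **Alpha.** 0.05 appears only in the power text of the Simulation Study, without sidedness. There, with 60 per group, "power to detect the difference between 0.25 and 0.50 is 81.80" percent.

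**The concern.** Two analyses of one outcome, with no order between them and no threshold for either, leave the definition of a positive trial open until the data are seen. The final comparison also uses an arm chosen partly because it looked best at the interim, and the interim patients are counted again at the end. An unadjusted final test, Bayesian or frequentist, therefore has more than its nominal chance of a false claim. The plan sets out to show acceptable Type I and Type II error, but the figure it gives stops at the pruning step. What is at stake is whether a positive result on the retained arm carries the error rate a reader would assume.

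**Working it through.** **Inputs from the Simulation Study:** placebo response 0.25; 80 patients at the interim and 80 after; on average 60 in the retained arm and 60 on placebo; Beta(1,1) priors; alpha 0.05. **Assumptions:** 20 per arm at the interim, then 40 more in each of the two remaining arms; dropout and week-8 re-randomisation ignored.

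**1. The plan's power figure.** Pooled-variance formula for two proportions, n = 60, 0.25 vs 0.50, mean rate 0.375:

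- SE under no difference = √(2 × 0.375 × 0.625 / 60) = 0.0884
- SE under the alternative = √((0.1875 + 0.25) / 60) = 0.0854
- Power = Φ((0.25 − 1.96 × 0.0884) / 0.0854) = Φ(0.899) = 81.6%

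Exact enumeration of the uncorrected two-sided chi-square gives 81.8%, the stated value. A one-sided 0.05 test would give 89.0%. The stated power is therefore that of a two-sided 0.05 chi-square and of no Bayesian rule.

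**2. Borderline results, placebo 15/60.** z = difference / √(p̄(1 − p̄) / 30). For 24/60: 0.15 / √(0.325 × 0.675 / 30) = 1.754, p = 0.079. Posteriors by numerical integration:

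| Treatment | chi-square p | P(diff>0) | P(diff>10 points) |
|---|---|---|---|
| 24/60 | 0.079 | 0.959 | 0.708 |
| 25/60 | 0.053 | 0.973 | 0.770 |
| 26/60 | 0.034 | 0.982 | 0.823 |

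The first two rows are negative by chi-square and positive at an assumed 0.95 cutoff. At 0.975 they are negative on both.

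**3. How often the analyses disagree.** Exact enumeration, 60 per arm, against a favourable two-sided p<0.05. The cutoffs are assumed, because the plan gives none for the final analysis.

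| Bayesian rule | 0.25 vs 0.40 | 0.25 vs 0.45 | 0.25 vs 0.50 |
|---|---|---|---|
| P(diff>0)>0.95 | 12.0% | 11.4% | 7.7% |
| P(diff>0)>0.975 | 1.3% | 0.9% | 0.4% |
| P(diff>0)>0.99 | 14.5% | 15.3% | 12.0% |
| P(diff>10 points)>0.80 | 4.0% | 2.2% | 0.7% |

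**4. False positives with the interim step included.** 25% response in all arms, selection and aspirin fallback as written, then 60 vs 60; 200,000 simulated trials. Wording A requires one arm with P(diff<10%)<0.20. Wording B fails only if the joint probability that all differences are under 10% exceeds 0.80. The first column is a fixed 60 vs 60 comparison without selection.

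| Final rule, favourable direction | No selection | A | B |
|---|---|---|---|
| Chi-square, two-sided 0.05 | 2.6% | 3.7% | 4.8% |
| P(diff>0)>0.975 | 2.4% | 3.4% | 4.4% |
| P(diff>0)>0.95 | 4.9% | 6.4% | 8.4% |
| Chi-square or P>0.95 | 4.9% | 6.4% | 8.4% |
| P(diff>0)>0.988 | – | 1.8% | 2.3% |

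The last two rules at 0.95 coincide because every favourable chi-square result also passes 0.95. At 0.988 the rate stays below 2.4% for common response rates of 20–35%.

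**5. Price in Scenario 2 (0.25, 0.30, 0.30, 0.50).** Overall success is 54% (A) or 74% (B) with the uncalibrated chi-square, and 49% or 65% with P(diff>0)>0.988.

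**Limit of the reconstruction.** Under no effect it finds a decisive difference in about 13% of trials (A) or 85% (B), not the stated 0.5%. The ranges thus rest on the rule as written, not on the sponsor's program.

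**The case against.** Several points on the other side stand.

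- The size of the disagreement depends on a cutoff the plan does not contain. A reader might infer that the same data would often be called both positive and negative. At 0.975, the natural match to a two-sided 0.05 test, the analyses differ in at most 1.3% of trials in the scenarios run. Carrying the plan's own 10-point, 0.80 criterion to the final analysis makes 24/60 and 25/60 negative on both methods.
- A reader might infer that only the Bayesian side lacks a rule. No decision alpha is stated for the chi-square either; two-sided 0.05 is inferred from the power figures.
- A reader might take the no-adjustment sentence as an excuse for leaving the final decision uncontrolled. It concerns interim analyses and says nothing on how the final claim is made.
- Both analyses are prespecified, and the plan describes the drop-the-loser design as useful in phase II development. Posterior statements are legitimate output there, and the background section calls Bayesian analysis the recommended strategy for adaptive trials. That preference still supplies neither precedence nor a success criterion.

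What survives is the missing precedence, the missing thresholds, and the lack of an error rate for the final claim.

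**Conclusion.** The concern holds in a limited form. The plan does not say which analysis decides or at what threshold, and its Type I figure covers pruning only, so its statement that error rates are appropriate is not shown for the final efficacy decision. With selection included, the two obvious unadjusted rules give about 3.4–4.8% favourable false positives against 2.5% nominal. A 0.95 posterior rule, used alone or as a second route to success beside the chi-square, gives 6.4–8.4%.

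It would be tempting to conclude that naming the chi-square settles the matter. It removes the ambiguity but leaves the selection inflation. Nor is the stated power wrong: it reproduces, for a fixed comparison of 60 vs 60. All simulated ranges are illustrative, given the assumptions on interim allocation, dropout and re-randomisation.

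**What to change.** - In General Data Analytic Strategies, name one deciding analysis for the retained arm vs placebo. Label the other supportive, with no separate success claim.
- Fix the deciding threshold in advance, with sidedness or effect size, calibrated by simulation that includes the pruning step under a single stated wording of the rule. This applies equally to a chi-square critical value and to a posterior cutoff. As a guide, P(diff>0) above about 0.988 meets a 2.5% favourable-direction target here.
- In the Simulation Study and the interim-analysis paragraph, report Type I error and power for that final rule, and say that 0.005 refers to pruning only.
- If the unadjusted 0.05 chi-square is kept as the deciding test, state its post-selection favourable false-positive rate, about 4–5%.

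The cost is one more simulation run, some SAP wording and a less favourable stated power: in Scenario 2, about 49–65% at 0.988 against 54–74% for the uncalibrated chi-square. Part of that gap is the price of controlling an error rate the chi-square exceeds.
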